8.1.11 Dispensing

Only a 28-day supply may be dispensed at one time. Sites may not mail lenalidomide to patients.

Rev. 7/11

8.1.12 Patient Care Implications and Counseling

Risks Associated with Pregnancy

Lenalidomide is structurally related to thalidomide. Thalidomide is a known human teratogenic active substance that causes severe life-threatening birth defects. An embryofetal development study in animals indicates that lenalidomide produced malformations in the offspring of female monkeys who received the drug during pregnancy. The teratogenic effect of lenalidomide in humans cannot be ruled out. Therefore, a risk minimization plan to prevent pregnancy must be observed.

Definition of female of childbearing potential (FCBP)

This protocol defines a female of childbearing potential as any woman, regardless of sexual orientation or whether they have undergone tubal ligation, who meets the following criteria: 1) has not undergone a hysterectomy or bilateral oophorectomy or 2) has not been naturally postmenopausal (amenorrhea following cancer therapy does not rule out childbearing potential) for at least 24 consecutive months (i.e., has had menses at any time in the preceding 24 consecutive months).

Before starting study drug:

Female Subjects:

- FCBP must have two negative pregnancy tests (minimum sensitivity of 25 mIU/mL) prior to starting study drug. The first pregnancy test must be performed within 10-14 days prior to the start of study drug and the second pregnancy test must be performed within 24 hours prior to the start of study drug. The subject may not receive study drug until the Investigator has verified that the results of these pregnancy tests are negative.

Male Subjects:

- Must agree to use a latex condom during sexual contact with females of childbearing potential while participating in the study and for at least 28 days following discontinuation from the study even if he has undergone a successful vasectomy.

All Subjects:

- Only enough lenalidomide for one cycle of therapy may be dispensed with each cycle of therapy.
- If pregnancy or a positive pregnancy test does occur in a study subject or the partner of a male study subject during study participation, lenalidomide must be immediately discontinued.

Counseling

- In investigational studies where lenalidomide is supplied by the NCI, patients will be counseled by a qualified healthcare professional (including but not limited to, nurses, pharmacists and physicians). Two healthcare professionals at each site will be trained by Celgene in requirements specific to counseling of

subjects (investigators cannot counsel patients as part of this requirement). Refer to specific protocol sections for more information about training requirements.

- Once trained, these healthcare staff will counsel subjects prior to medication being dispensed to ensure that the subject has complied with all requirements including use of birth control and pregnancy testing (FCBP) and that the subject understands the risks associated with lenalidomide. This step will be documented with a completed Lenalidomide Education and Counseling Guidance Document ([Appendix XI](#)) and no drug will be dispensed until this step occurs. Counseling includes verification with the female patient that required pregnancy testing was performed and results were negative. A Lenalidomide Information Sheet ([Appendix XII](#)) will be supplied with each medication dispense.”

Rev. 11/13
Rev. 7/11

8.2 Epoetin Alfa (NSC# 628281)

Experience in Subjects with Cancer

A randomized controlled clinical study, previously summarized in the label and published in 2005, entitled, “Maintaining Normal Hemoglobin Levels With Epoetin Alfa in Mainly Nonanemic Patients With Metastatic Breast Cancer Receiving First-Line Chemotherapy: A Survival Study” (BEST) evaluated 939 women with metastatic breast cancer receiving chemotherapy. Patients received either weekly Epoetin alfa or placebo for up to a year. This study was designed to show that survival was superior when Epoetin alfa was administered to prevent anemia (maintain hemoglobin levels between 12 and 14 g/dL or hematocrit between 36% and 42%). The study was terminated prematurely when interim results demonstrated that a higher mortality at 4 months (8.7% vs. 3.4%) and a higher rate of fatal thrombotic events (1.1% Epoetin alfa vs. 0.2% placebo) in the first 4

months of the study were observed among patients treated with Epoetin alfa. Based on Kaplan-Meier estimates, at the time of study termination, the 12-month survival was lower in the Epoetin alfa group than in the placebo group (70% vs. 76%; HR 1.37, 95% CI: 1.07, 1.75; $p = 0.012$).⁶

A multicenter, randomized, double-blind, placebo-controlled trial in which patients with advanced non-small cell lung cancer unsuitable for curative therapy were treated with Epoetin alfa targeting hemoglobin levels between 12 and 14 g/dL or placebo. Following an interim analysis of 70 of 300 patients planned, a significant difference in median survival in favor of patients in the placebo group was observed (63 vs. 129 days; HR 1.84; $p = 0.04$).⁷

A preliminary report from a clinical study (DAHANCA) evaluated 522 patients with primary squamous cell carcinoma of the head and neck receiving radiation therapy. Patients were randomized to darbepoetin alfa (a different erythropoietin drug) or placebo. An interim analysis in 484 patients demonstrated a 10% increase in locoregional failure rate among darbepoetin alfa-treated patients ($p = 0.01$). At the time of study termination, there was a trend toward worse survival in the darbepoetin alfa-treated arm ($p = 0.08$).⁸

A recently completed phase 3, double-blind, randomized, placebo-controlled 16-week clinical study evaluated 989 patients with active malignant disease not receiving chemotherapy or radiation therapy. There was no evidence of a statistically significant reduction in proportion of patients receiving RBC transfusions. In addition, there were more deaths in the darbepoetin alfa treatment group [26% (136/515)] than the placebo group [20% (94/470)] at 16 weeks (completion of treatment phase). With a median survival follow up of 4.3 months, the absolute number of deaths was greater in the darbepoetin alfa treatment group [49% (250/515)] compared with the placebo group [46% (216/470); HR 1.29, 95% CI: 1.08, 1.55].⁹

NOTE: Refer to epoetin alfa package insert for more information.

8.2.1 Other Names

Erythropoietin, rhu-erythropoietin, EPO, Epogen, Procrit.

8.2.2 Classification

Colony stimulating factor; cytokine.

8.2.3 Mode of Action

Stimulates red cell production. It stimulates the division and differentiation of committed erythroid progenitors in the bone marrow.

8.2.4 Storage and Stability

Epoetin alfa is stored in the refrigerator (2-8°C). Do not freeze or shake. If the epoetin alfa solution freezes, it must not be used. The solution should be brought to room temperature prior to injection.

The 1 mL vial single-dose vial contains no preservative. Use one dose per vial. Do not re-enter vial; discard unused portions.

The 1 mL or 2mL multidose vials contain preservative. Store at 2° to 8° C after initial entry and between doses. Discard 21 days after initial entry. Epoetin alfa should be drawn up into a plastic syringe and

administered subcutaneously according to standard sterile techniques.

8.2.5 Dose Specifics

60,000 subcutaneously weekly. Repeated every 28 days for four cycles.

8.2.6 Preparation

Usually single-dose vials are administered undiluted, although preservative-free solutions may be mixed with bacteriostatic NS containing benzyl alcohol 0.9% in a 1:1 ratio.

Admixing is not necessary when using the multidose vials of epoetin alfa containing benzyl alcohol. Do not dilute or administer in conjunction with other drug solutions.

8.2.7 Route of Administration

Subcutaneous

8.2.8 Availability

Those patients who had previously received Procrit from the NCI will be switched to the commercially supplied Procrit.

As of Addendum #13, all patients will receive epoetin alfa (Procrit) through the commercial channels, or through the ESA Apprise Oncology Program.

Vial sizes available:

Single-dose vial: 2000, 3000, 4000, 10,000, and 40,000 Units/1 mL (3).

Multidose vial containing benzyl alcohol: 20,000 Units/2 mL and 20,000 Units/1 mL (3).

NOTE: See Section [8](#) for updated drug ordering instructions.

8.2.9 Incompatibilities

Epoetin Alfa is contraindicated in subjects with the following:

- Uncontrolled hypertension
- Known hypersensitivity to the active substance or any of the excipients

8.2.10 Side Effects

1. Fever (29%).
2. Gastrointestinal: Diarrhea (21%), nausea (17%), vomiting (17%).
3. Cardiovascular: Edema (17%), hypertension with dialysis patients.
4. Neurologic: Paresthesia (11%); increased incidence of seizures in dialysis patients.
4. Dermatologic: Local erythema; rash (mild, rare, and transient).

Rev. Add15

Rev. 6/13

Rev. 5/17

Rev. Add15

5. Thrombotic events: Pulmonary embolism, cerebral vascular accident.
6. Other: Potential to increase tumor growth.

Thrombovascular Events

TVEs, such as myocardial ischemia, myocardial infarction, cerebrovascular accidents (cerebral hemorrhage and cerebral infarction), transient ischemic attacks, deep venous thrombosis, arterial thrombosis, pulmonary emboli, retinal thrombosis, and clotting of an artificial kidney or shunt have been associated with the use of erythropoietic agents as reflected in the labeling of all currently marketed products. Additionally, there is a potential for an increased rate of TVE occurrence when recombinant human erythropoietin is used in non-anemic subjects. Published findings from a study evaluating survival in subjects with cancer has indicated that there may be an increased risk of TVE associated with recombinant human erythropoietin treatment of non-anemic cancer subjects.¹⁰

In summary, the occurrence of TVE is associated with epoetin alfa treatment whether used in anemic or non-anemic subjects.

8.2.11 Nursing Implications

1. Monitor for central venous catheter occlusion or generalized thrombosis.
2. Administer antipyretics, antiemetics and analgesics as needed. Diphenhydramine PO may decrease erythema at the subcutaneous injection site.
3. Inform patient of possible side effects.
4. Encourage patient to keep scheduled laboratory visits, as frequent blood tests are needed to determine the correct dose of epoetin alfa.
5. Monitor blood pressure and heart rate prior to each dose of epoetin alfa.
6. Self-administration of epoetin alfa is not permitted for patients on protocol treatment.

8.2.12 Allergic Responses

There may be a risk of developing an allergic reaction to rhu-erythropoietin. Rare allergic symptoms following epoetin alfa treatment (e.g., skin rash, itching and hives) have been reported. It is possible for more serious allergic reactions to occur. These possible reactions include a whole body rash, shortness of breath, wheezing, sudden drop in blood pressure, swelling around the mouth or eyes, rapid pulse or sweating. If a serious allergic or anaphylactic reaction occurs, epoetin alfa should be immediately and permanently discontinued and appropriate therapy should be administered.

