5.1.2 Arm B (Lenalidomide + Epoetin Alfa)

Lenalidomide 10 mg po/day on days 1-21 followed by 7 days of no therapy and epoetin alfa 60,000 units subcutaneously (s.c.) every week. Repeat cycles every 28 days for a total of 4 cycles. (Refer to Section [5.1.3](#) for further treatment).

Blood pressure and heart rate measurements will be assessed prior to each dose of epoetin alfa.

Patients with a pretreatment platelet count of 50,000-99,000/mcL or an ANC of 500-999/mcL will receive a lenalidomide dose of 5 mg po/day on days 1-21.

5.1.3 Patients on Arm A or Arm B who achieve a Major Erythroid Response (MER) according to modified International Working Group (IWG) criteria described in Section [6](#) may continue the assigned treatment in the absence of limiting toxicity or disease progression.

Patients on Arm A who do not achieve a MER will have the option to cross over to Arm B (see Section [5.2](#)). If they choose not to cross over, they will then discontinue protocol treatment.

Patients on Arm B who do not achieve a MER will discontinue treatment.

If the treating MD and/or PI feels that the subject is receiving benefit from study (in the way of decreasing RBC transfusion frequency and/or HGB increase outside RBC transfusion influence) but does not meet MER, subjects may remain on treatment if they have achieved a **minor** erythroid response until demonstrating signs of lack of continued response (example: increase in RBC transfusion dependence, or decreased HGB on consistent basis outside of the influence of RBC transfusions). See Section [6.1.2.3](#) for reference. If there are questions regarding this item, please have the treating MD and/or PI email [name] for further discussion on a case by case basis.

Treatment with white cell growth factors is allowed for the management of neutropenia at the discretion of the treating investigator.

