5.5.7 Dose Modifications for Other Adverse Events

Dose interruption and modification guidelines for other adverse events are in Table 2. Lenalidomide should be held for any ≥ grade 3 adverse events with suspected drug association until resolution to < grade 2. For any patient who does not experience resolution to < grade 2 within 6 weeks should be removed from protocol treatment and complete all off-study evaluations. For patients with thromboembolic events, both agents should be discontinued and not resumed until resolution with proper prophylaxis according to the discretion of the treating investigator.

NOTE: Patients will be removed from study treatment if lenalidomide is held for > 6 weeks for treatment-related toxicity.

NOTE: For patients on Arm B, epoetin alfa will continue while lenalidomide is being held for toxicity.

Rev. 1/10

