5.5.8 Dose Reduction for Patients with Renal Insufficiency

Defined as creatinine >1.5 mg/dl that does not resolve to grade 1.

Rev. 6/11

[Deleted in Addendum #4]

- Patients with CLcr <60 mL/min and ≥ 30 mL/min should be monitored closely for possibly excess myelosuppression or other toxicity, and dose reduce by 50% upon recovery.

Rev. 6/11

[Deleted in Addendum #4]

Table 2: Dose Modifications for Lenalidomide

System	NCI CTCAE Grade	Action
Coagulation	Venous thrombosis/embolism ≥ Grade 3	
 Hold (interrupt) dose and start anticoagulation; resume lenalidomide at investigator's discretion (maintain dose level).
Skin	Desquamating (blistering) rash	
 Discontinue study treatment.
	Non- desquamating rash Grade 2	
 If Grade 2, interrupt lenalidomide therapy. Resume lenalidomide when the rash resolves to ≤ Grade 1 (decrease one dose level).
	Grade ≥ 3	
 Hold lenalidomide study drug.
Neurology	Neuropathy Grade 3	
 If Grade 3, interrupt lenalidomide 3 therapy. Resume lenalidomide when the neuropathy resolves to ≤ Grade 1 (decrease one dose level).
	Grade 4	
 Hold lenalidomide study drug.
Allergy	Allergic reaction Grade 2	
 If Grade 2, interrupt lenalidomide therapy. Resume lenalidomide when symptoms resolve to ≤ Grade 1 (decrease one dose level).
	≥ Grade 3	
 Hold lenalidomide study drug.
Gastrointestinal	Constipation ≥ Grade 3	
 Hold (interrupt) dose. Initiate bowel regimen, and resume lenalidomide when constipation resolves to ≤ grade 2 (decrease one dose level).
Endocrine	Hyperthyroidism or hypothyroidism	
 Interrupt lenalidomide and initiate appropriate medical therapy. Resume lenalidomide at investigator's discretion (maintain dose level).
Cardiac Arrhythmias	Sinus bradycardia/other cardiac arrhythmia Grade 2	
 Hold (interrupt) dose. Follow at least weekly. If the toxicity resolves to ≤ grade 1 resume at next lower dose level.
	≥ Grade 3	
 Hold lenalidomide study drug.

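### For a serious allergic reaction in Arm B, Section 8.2.12 stops epoetin alfa permanently, while Table 2 and the Section 5.5.7 NOTE together keep it going

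*Combined protocol and SAP*

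**What the plan says.** Section 8.2.12 (epoetin alfa, Allergic Responses) begins: "There may be a risk of developing an allergic reaction to rhu-erythropoietin". Further on it instructs: "If a serious allergic or anaphylactic reaction occurs, epoetin alfa should be immediately and permanently discontinued". That sentence does not say which drug must be suspected, and it gives no CTCAE grade. Section 8.2.9 states "Epoetin Alfa is contraindicated in subjects with the following" and lists two conditions: uncontrolled hypertension, and known hypersensitivity to the active substance or an excipient.

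The toxicity rules are in Section 5.5. The table there is titled "Table 2: Dose Modifications for Lenalidomide". Its allergy row, for grade 3 or higher, reads "Hold lenalidomide study drug" and does not mention epoetin. The NOTE at the end of Section 5.5.7 reads: "For patients on Arm B, epoetin alfa will continue while lenalidomide is being held for toxicity". Section 5.5.7 makes one exception that covers both drugs: "For patients with thromboembolic events, both agents should be discontinued and not resumed until resolution". Section 5.5.5, which sets out epoetin dose changes, deals only with hemoglobin and does not refer to Section 8.2.12.

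On blood pressure, Section 5.1.2 says: "Blood pressure and heart rate measurements will be assessed prior to each dose of epoetin alfa". Section 8.2.11 repeats the requirement. Neither gives a threshold or an action.

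**The concern.** Two sites, each following the protocol, could handle the same Arm B patient in opposite ways after a serious allergic reaction. One, reading Section 8.2.12, would stop epoetin for good. The other, reading Table 2 and the NOTE, would hold lenalidomide and give the next weekly epoetin dose. The main stake is patient safety, since one of the two readings re-exposes the patient to a possible cause of the reaction. The lesser stake is that epoetin exposure, the only planned treatment difference between the arms, would depend in these patients on which section the site consulted.

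**Working it through.** The plan states no figure on this point and no arithmetic applies. The check sets the instructions side by side for one patient: on the combination, with an allergic reaction of grade 3 or higher. Section 8.2.12 speaks of serious reactions without a grade, so treating serious as grade 3 or higher is an assumption made to compare the two rules.

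| Source | Lenalidomide | Epoetin alfa |
|---|---|---|
| Table 2, allergy row | Hold | Not mentioned |
| 5.5.7 NOTE | Already held for toxicity | Continue |
| 8.2.12 | Not mentioned | Stop at once, permanently |

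**Step 1: does the NOTE apply?** Its only trigger is that lenalidomide is being held for toxicity, and the Table 2 allergy row creates that hold. The NOTE has no allergy exception. The drafters did write a two-drug exception in the same section for thromboembolic events, so silence on allergy cannot safely be read as an implied exception. Table 2 also ends all study treatment for desquamating rash but holds only lenalidomide for allergy, which points the same way.

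**Step 2: does attribution separate the rules?** There are three cases.
- Lenalidomide alone suspected: Table 2 and the NOTE apply. Section 8.2.12 applies on its literal wording, but arguably not if read with its opening sentence about reactions to epoetin.
- Epoetin alone suspected: Section 8.2.12 applies. The Table 2 allergy row has no attribution condition, unlike the catch-all row, which is limited to lenalidomide-related toxicity. The Section 5.5.7 text asks only for suspected drug association and does not name the drug. Read literally, lenalidomide is held and the NOTE is triggered.
- Cause unclear or shared: both rules apply and they are opposite. This case is realistic, because the adverse event list in Section 5.4 includes allergic reaction and anaphylaxis for lenalidomide, and Section 8.2.12 warns of the same for epoetin.

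Attribution therefore narrows the conflict but does not remove it, and no section says what to do in the third case.

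**Step 3: who is covered?** Patients randomized to Arm B, and Arm A patients who cross over to Arm B under Section 5.2.

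**Step 4: does any rule break the tie?** Section 5.7.3 lets the investigator end treatment for an event that could cause severe or lasting harm. This is a general discretion and does not say which specific epoetin instruction governs. No section ranks 5.5 above 8.2, or the reverse.

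**Step 5: hypertension.** Section 8.2.9 contraindicates epoetin in uncontrolled hypertension, and eligibility criterion 3.1.1.12 applies this at entry. Table 2 has no hypertension row. The NOTE could meet Section 8.2.9 only if hypertension reached grade 3 or higher, was judged lenalidomide-related, and led to a lenalidomide hold under the catch-all row. Section 5.4 lists hypertension for lenalidomide, so this route is possible but indirect. Otherwise, what is missing is an action tied to the pre-dose blood pressure reading.

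**The case against.** The strongest reply is that the rules belong to different drugs. Section 8.2.12 opens with reactions to epoetin, Table 2 is titled for lenalidomide, and a clinician would follow the rule for the suspected drug. There are also safeguards. Section 8.2.9 separately contraindicates epoetin in known hypersensitivity, known epoetin allergy is excluded at entry (3.1.1.24), Section 8.2 refers to the package insert, Section 5.7.3 allows treatment to be stopped, and Section 8.2.11 bars self-administration, so each dose is given by a health professional.

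Much of this stands. A reaction clearly due to one drug would probably be handled sensibly, and the safeguards make an inappropriate dose less likely. But the drug-by-drug reading fails at the NOTE, which is an epoetin instruction triggered by a lenalidomide hold, and it gives no answer when the cause is unclear or shared. The safeguards rely on a clinician to override a written instruction; they do not correct it.

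A reader might also infer more than the text supports:
- That Table 2 itself continues epoetin. It does not mention epoetin; only the NOTE does.
- That uncontrolled hypertension is a second contradiction of the same kind. No section says to continue epoetin in hypertension by name, and the collision needs the indirect route in step 5.
- That Section 5.5 is the controlling dosing section. No section says so, and Section 8.2.5 also states epoetin dosing.

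**Conclusion.** The concern holds for allergic reactions. As written, Section 8.2.12 on one side, and the Table 2 allergy row with the Section 5.5.7 NOTE on the other, give opposite epoetin instructions for a patient on the combination with a serious allergic reaction. The conclusion rests on reading serious as grade 3 or higher, and it is firmest where the responsible drug is uncertain. The blood pressure point is a gap in the instructions, not a contradiction.

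A reader might want a number of affected patients, but the documents do not support one. Section 5.4 places allergic reaction and anaphylaxis in its under-3% category for lenalidomide, and Section 8.2.12 calls allergic symptoms after epoetin rare. Neither gives a rate of serious reactions on the combination, or the share with uncertain cause. Events are probably few, and nothing here shows a material effect on the primary comparison of major erythroid response. The reason to act is safety and uniform treatment. Which instruction is clinically right is outside this review.

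**What to change.** In the next addendum, reconcile the Section 5.5.7 NOTE, the Table 2 allergy row, Section 8.2.9 and Section 8.2.12 so that all four carry the same epoetin instruction for allergic reactions in patients on Arm B treatment, including crossovers. The text should say what applies when the responsible drug is uncertain or both are suspected, and should express serious reactions on the grading scale that Table 2 uses. The clinical leads decide the instruction; the requirement here is only that the sections agree.

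In the same addendum, state which rule, if any, the pre-dose blood pressure reading in Sections 5.1.2 and 8.2.11 feeds, and how the NOTE relates to Section 8.2.9 if lenalidomide is held for hypertension. The content is again for the clinical leads.

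The cost is protocol wording and notice to sites. The reconciliation itself needs no new visits or tests, since blood pressure is already measured before each epoetin dose, and the sample size and analysis plan do not change.
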